### **Treatment Assignment Procedures**

Eligible, consented, and enrolled participants will be randomized to YST or AC. To control for type and stage of cancer, randomization will occur within both type (colon, rectal/other better prognosis GI cancers, poorer prognosis cancers) and stage (localized stages II/III or metastatic stage IV). There is not a sample size goal within strata. Given this relatively small preliminary study, it was deemed more efficient and enabled tighter control over known influences on outcome to stratify rather than to use statistical control via covariate analysis. The other alternative would have been to use only a single type/stage of cancer, which was not feasible due to too few cases at VICC and CCC-WFU. The population of the cancer patients with the types/stages selected was sufficient at VICC and CCC-WFU to enable randomization within thus increasing generalizability potential.

Randomization (1:1) lists within each strata will be generated via a permuted block program developed and executed by the study biostatistician with blocks of random sizes between 2 and 6. The randomization lists will be held by a staff member (not involved with data collection) who will allocate each participant to study group. STM who are collecting data will not be informed of group assignment.

### **9.3 Definition of Populations**

Per our description above, we used the revised CONSORT 2010 guidelines for intention-to-treat (ITT) analysis of randomized control trials in our sample considerations. Those guidelines dropped specific ITT in favor of clear descriptions of exactly who would be (or was) included in the analysis per our specification above. We also took into account considerations for minimizing missing data within the context of ITT specified by White et al. We have incorporated flexible windows for the data collection in our protocol and are allowing for possible randomly missing interim assessments. Therefore the population to whom these preliminary efficacy

findings will be generalizable to will be that represented by the sample meeting our requirements for inclusion in the ITT sample (see above).

#### **9.4 Interim Analyses and Stopping Rules**

There are no interim analyses planned for the primary and secondary outcomes in this clinical trial. Summaries of process variables (i.e., recruitment, adherence, data collection, retention, safety) will be conducted on a rolling basis as the study progresses. The PI will present data on subject accrual with research mentors and Independent Monitoring Committee (IMC). We anticipate recruitment on average of 1-2 patients per month or 18 patients in one year completing enrollment over the next 30 months. Fidelity of implementing the interventions will also evaluated during the study period. If we document fidelity less than 80% during the clinical trial, than interventionists will undergo further training with subsequent re-evaluation demonstrating sufficient fidelity.

Futility analyses for efficacy or safety will not be conducted in this pilot study. SAE's related to the intervention will suspend enrollment and/or the study intervention until a safety review is convened (either routine or ad hoc) by IMC to determine whether the study intervention should continue per protocol, proceed with caution, be further investigated, discontinued, or be modified and then proceed. If SAEs events are related to the interventions, then the relevant intervention protocol will be modified to avoid adverse events. If the frequency of non-serious adverse events is higher than anticipated or alters the benefit risk ratio as determined by the IMC and PI, the study investigators will also modify the relevant intervention protocol. Two or more specific adverse events among participants will prompt modification of the protocol.

#### **9.5 Outcomes**

The STM collecting outcome data will be masked to the participant's intervention group assignment.

##### **9.5.1 Primary Outcome**

**Fatigue (recalled)** "in the past seven days" will be assessed with the 7-item measure of Fatigue from the Patient-Reported Outcomes Measurement Information System (PROMIS)-Cancer specifically designed for use in cancer patients (item responses: 1 = never, 5 = always). This measure was selected for the primary outcome (at 10 weeks) because it is standardized, validated in people with cancer, and PROMIS is supported by NCCIH and the National Cancer Institute.

##### **9.5.2 Secondary Outcomes**

**Depressive Symptoms (recalled)** will be assessed with the standardized 10-item PROMIS-Cancer Depressive symptoms short-form, which was designed to be valid for cancer patients.

**Fatigue and Depressive Symptoms (daily)** "in the last day" will be assessed with 3 items selected from the PROMIS measures of fatigue and depression validated for use

in daily diaries. This subset of items was selected to minimize patient burden and because they were the items most sensitive to day-to-day changes. Response options are the same as in the recalled measures.

**Psychological Stress (recalled)** will be assessed by the 10-item Perceived Stress Scale (PSS). The PSS has 2 factors (stress and counter stress) and is valid for use with cancer patients.

**Psychological Stress (daily)** will be assessed with two items from the 4-item PSS that would be on the same factor to optimize internal consistency. The PSS has been successfully applied daily.

**Regulation of Psychological Stress (recalled)** will be determined by ratings on four of the seven factors of the Cancer Behavior Inventory, which assess self-efficacy for stress management ( $\alpha = 0.86$ ), coping with treatment-related side-effects ( $\alpha = 0.82$ ), accepting cancer/maintaining positive attitude ( $\alpha = 0.86$ ), and affective regulation ( $\alpha = 0.81$ ).

**Regulation of Psychological Stress (daily)** will be assessed with the 3-item serenity subscale from the Positive and Negative Affect Schedule-Expanded Form.

**Circadian disruption (recalled)** will be assessed with measures of activity and rest. Activity will be measured using the 3-item Godin's leisure score index (LSI), previously used with GI cancer patients during chemotherapy. Rest will be assessed with the 8-item PROMIS sleep disturbance short-form.

**Circadian Disruption (daily)** will be assessed with actigraphy. Circadian disruption is defined as a ratio of nighttime activity to daytime activity with higher scores indicating greater circadian disruptions.

**Inflammation.** Inflammatory cytokines (i.e., IL-6, sTNF-R1, TNF- $\alpha$ ) that have been associated with fatigue during treatment for gastrointestinal cancer and influenced by yoga practice will be measured in plasma extracted from whole blood drawn during regularly scheduled clinical blood draws.

The following table provides a summary of which study week study constructs will be assessed.

#### Study Constructs and Times Measured

Weeks	0	0-2	8	8-10	10	14
Outcomes						
Fatigue ( primary in bold text )	R	Daily	R	Daily	R	R
Depressive Symptoms	R	Daily	R	Daily	R	R
Mechanisms						
Psychological Stress	R	Daily	R	Daily	R	R
Regulation of Psychological Stress	R	Daily	R	Daily	R	R
Circadian Disruption	R	Daily	R	Daily	R	R

Inflammation	✓	✓
Process		
Intervention Home Practice	*	Daily
Outcome Expectancies	✓	
Efficacy Beliefs	✓	
Adherence		All Measures
Qualitative Feedback		S
Descriptive		
Demographic/Clinical	✓	✓

R = recalled assessment; S = semi-structured interview; ✓ = collected

\*Paper diary will be kept throughout the intervention

## 9.6 Data Analyses

SAS will be used for statistical analysis. Graphical and descriptive statistical methods will be applied to examine the shapes of study data distributions and need to transform, if necessary, for inferential analyses. Per descriptions above, analyses will be conducted using intention-to-treat principles as stated in the CONSORT 2010 guidelines and flexible protocol elements to minimize missing outcome data. Missing data are expected to be of two types: 1) nonrandom (death, deteriorating condition, or other lost-to-follow-up) and 2) random (inability to make it into the clinic for one of the assessment periods). Because fatigue post-intervention is the most critical outcome assessment point, the 1st assessment (study entry) and the post-intervention assessment point at Week 10 after study entry will be required for inclusion in the hypothesis testing analysis. Randomly missing assessments at Week 10 will be handled within the statistical analysis described. Randomly missing item responses within study measures will be handled according to the instructions for each instrument when developed and validated. Missing data assessments and drop-out occurrences will be analyzed to inform future research. We do not expect those types of missing data to be random; therefore imputation procedures will not be conducted. Maximum Type I error of 0.05 (uncorrected and/or corrected as necessary) will be maintained for statistical significance and all analyses will be performed in consultation with [name].

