### **Sample Size and Population**

The target population is 44 participants, 22 in each group. Randomization will be stratified by type of cancer (colon, rectal/other better prognosis GI cancers, poorer prognosis cancers) and cancer stage (localized stages II/III or metastatic stage IV) to minimize differences between groups (6 strata total). We will add cancers of the small intestine, anus and appendix to our existing rectal cancer strata since the survival rates are similar. The cancer types with poorer prognoses will be put into the new strata (with <50% 5-year survival rate; cancers of the esophagus, stomach, pancreas, gallbladder, liver).

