Based on prior longitudinal work with patients from similar populations, we are anticipating approximately 15% dropout (from N=44). From previous research in a mixed sample of cancer patients, the variability in the values of the PROMIS 7-item fatigue measure used in this study is a standardized standard deviation of 8 points (Mean t-score=53.6). Effect sizes in preliminary studies of yoga for fatigue as compared to an active control in patients with cancer range from 0.33 to 1.50. This variability may be explained in part by study quality and patients' initial levels of fatigue. We expect that daily assessments of fatigue and depressive symptoms will detect these symptoms at their nadir and thus may be more sensitive to such phenomena than recalled measures. Therefore, it is important to obtain a good estimate of the variance of fatigue in this group to use in future studies. Power calculations for a subsequent larger study will be based on clinically meaningful differences between the groups on the primary outcome using estimates of SD. With a sample size of 44, the probability is 0.80 (80% confidence) that the estimate of the standard deviation (SD) will be no more than 10% of the true population SD below the true population SD; if the SD varies by group, there is 80% confidence that the estimate of the SD is no more than 14% below the true SD.

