### **10.3.3 Metrics**

Review of the rate of subject accrual and compliance with inclusion/exclusion criteria will occur monthly by the PI during the first three months and then every quarter (4 months) to ensure that a sufficient number of participants are being enrolled and that they meet eligibility criteria and the targeted ethnic diversity goals outlined in the grant proposal (Targeted/Planned Enrollment Table).

Adherence of participants will be evaluated by documentation of participation in interventions during chemotherapy. We will consider high adherence to the intervention if subjects participate in 80% of the in-person interventions. If on review, adherence is below this threshold, [name] will convene a conference call to discuss methods for improving adherence.

[name] or study staff will also review all data collection forms on an ongoing basis (i.e., quarterly) for data completeness and accuracy as well as protocol compliance. A

study member not involved in data collection will enter the data. At least ten percent of all data entered from questionnaires will be randomly selected and verified for accuracy against original source documents. Any discrepancies will be discussed with the Independent Monitors. Data will also be reviewed for outliers and to determine if values are missing at random prior to analysis. [name] will provide quarterly updates to the IMC and research mentors regarding patient accrual.

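### Section 9.6 gives expected non-random loss as its reason not to impute and adds no sensitivity analysis, so the Week 10 fatigue SD wanted for the next trial may be biased, probably low if the more fatigued leave

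*Combined protocol and SAP*

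**What the plan says.** Section 9.6 (Data Analyses) expects two kinds of missing data: non-random, through death, deterioration or other loss to follow-up, and random, through a missed clinic visit. It requires the baseline and Week 10 assessments for entry into the hypothesis-testing analysis. It also says that randomly missing Week 10 assessments will be dealt with inside the statistical model, which does not fit with that requirement. On missing assessments and drop-out it concludes: "We do not expect those types of missing data to be random; therefore imputation procedures will not be conducted". It promises to analyse drop-out for the benefit of later research, but names no sensitivity analysis.

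Section 9.2 makes a good estimate of the fatigue variance a main product of the pilot, to be used in powering a larger trial. It anticipates about 15% dropout from 44. It then gives a precision for all 44, to hold with probability 0.80: "the estimate of the standard deviation (SD) will be no more than 10% of the true population SD below the true population SD". For SDs that differ between the arms, the matching shortfall is 14% at the same confidence. Neither the visit nor the population is named. The primary outcome in 9.5.1 is fatigue at Week 10.

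Section 10.3.3 (Metrics) says that data will be reviewed "to determine if values are missing at random prior to analysis".

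**The concern.** The reasoning in 9.6 is incomplete in a way that matters. Standard imputation does not cure non-random loss, and to that extent the authors are right to distrust it. But analysing only the observed scores does not cure it either, because that analysis is the one exposed to the bias. The usual response is to use all available scores and then show how far the answer moves under stated departures from missing at random. The plan does neither.

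The SD is what the next trial will be sized on. If deteriorating patients are both more fatigued and more likely to be lost, the upper tail of Week 10 fatigue is thinned, the SD comes out too small, and the next trial is too small with it. The group difference can be biased as well. That is not quantified here, because the documents say nothing about how loss might differ by arm.

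The aim in 10.3.3 adds to the problem. Observed data can show that loss is not completely random, but cannot establish that it is random given what was observed. A check presented as settling that could reassure falsely.

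**Working it through.** **1. The plan's own figure.** Inputs from 9.2 and the Précis: N = 44, 22 per group, confidence 0.80, shortfall 10% pooled and 14% per group. For normal scores, P(s ≥ kσ) = 1 − F(df·k²; df), where F is the chi-square distribution function. The 80% bound on the shortfall is 1 − √(χ²₀.₂₀,df / df).

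- N = 44, k = 0.90: 0.808 (df 43) or 0.805 (df 42, pooled within groups). The 80% bound is 9.7% to 9.8%.
- n = 22, k = 0.86: 0.795 (df 21). The 80% bound is 14.2%.

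Both statements reproduce, provided nobody is lost.

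**2. The plan's own dropout, taken as random.** 0.85 × 44 = 37.4, so about 37 observed, or 18 to 19 per group.

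- n = 37: P(s ≥ 0.90σ) = 0.783 (df 36) or 0.780 (df 35). The 80% bound is 10.7% to 10.8%.
- n = 19 or 18: P(s ≥ 0.86σ) = 0.773 or 0.764. The 80% bound is 15.5% or 16.0%.

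This part follows from the documents alone, and it is small.

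**3. Informative loss (assumed mechanism).** Suppose a share q is lost because a latent propensity, correlated r with true Week 10 fatigue, exceeds a threshold. With c = Φ⁻¹(1 − q) and λ = φ(c)/(1 − q), the SD among those retained, relative to the truth, is √(1 − r²(cλ + λ²)).

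- All 15% informative: c = 1.0364, λ = 0.2743, cλ + λ² = 0.3595.
- Half informative (q = 0.075, the rest random and so without effect on the SD): c = 1.4395, λ = 0.1530, cλ + λ² = 0.2437.

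P(s ≥ 0.90σ) is simulated with 37 observed and is good to about 0.01. The comparison value under random loss is 0.78, not 0.80. The last column is the true power of a next trial planned at 80% on the low SD: Φ(2.80 × ratio − 1.96).

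| Loss | r | SD ratio | P(s ≥ 0.90σ) | Next-trial power |
|---|---|---|---|---|
| All 15% informative | 0.3 | 0.98 | 0.74 | 79% |
| | 0.5 | 0.95 | 0.65 | 76% |
| | 0.7 | 0.91 | 0.49 | 72% |
| Half informative | 0.3 | 0.99 | 0.75 | 79% |
| | 0.5 | 0.97 | 0.70 | 77% |
| | 0.7 | 0.94 | 0.60 | 75% |

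A different model, with 15% loss logistic in fatigue, gives the same pattern: log-odds of 0.5, 1.0 and 2.0 per SD give SD ratios of 0.98, 0.95 and 0.89, and probabilities of 0.75, 0.66 and 0.44.

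**4. Other directions.** If the middle 15% of fatigue scores were lost, the SD ratio would be 1.08, so the bias would be upward. If the SD were taken at baseline, where scores are collected before randomisation, loss by Week 10 would not affect it.

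**5. Size of a sensitivity shift.** Take the SD of 8 in 9.2 and 15% lost. If loss is in fact random, adding 10 T-score points to those lost gives √(64 + 0.15 × 0.85 × 100)/8 = √76.75/8 = 1.095. The SD is inflated by 9.5%, and the next trial by 76.75/64 = 1.20, or 20%.

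**The case against.** A reader might infer that the Week 10 SD is biased low and that the 9.2 statement fails. The documents do not support that. They give neither the strength nor the direction of any link between loss and fatigue, they expect random loss as well, and 9.2 is arithmetically right for 44. The higher correlations are also demanding: with all 15% lost this way, r = 0.7 puts those lost (1.554 + 0.274) × 0.7 = 1.28 SD above those retained, about 10 T-score points at an SD of 8.

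The target is open too. Sections 9.2 and 9.3 direct the efficacy findings to participants with baseline and Week 10 data, and for that population the observed SD is the right quantity. Loss is also limited by design. Assessments are mailed when chemotherapy slips by more than two weeks (6.2), and follow-up is sought remotely after a change of treatment location (6.2.5). Reasons for drop-out are recorded, and 9.2 wants completers compared with non-completers.

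These points stand and limit the finding to a risk. They do not remove it. Describing drop-outs corrects no estimate. Section 6.2.5 requires no evaluations of other early discontinuers. A larger trial must randomise patients before it knows who will complete, so a completer SD does not obviously serve it. That 9.2 leaves population and visit unstated is itself a reason to amend.

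It is also fair to say that a model alone may recover little. In one simulation at r = 0.7, using Weeks 0 and 8 moved the SD ratio only from 0.91 to 0.93. The amount depends on between-visit correlations that the documents do not give, which is why a shift analysis is needed as well.

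**Conclusion.** The concern holds as a gap in the plan, not as a demonstrated bias. Section 9.6 anticipates informative loss, analyses only those observed at Week 10, and provides nothing to show how much that matters. If the more fatigued leave, the Week 10 SD is likely too low and the 80%/10% statement can fail. The SD shortfall is about 2% to 9% if all 15% loss is informative and about 1% to 6% if half is, for an assumed correlation of 0.3 to 0.7 and an SD meant to describe all randomised participants at Week 10. What follows without any assumed mechanism is smaller: at about 37 observed, the 80% bounds become about 11% pooled and about 16% per group.

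**What to change.** 1. **Section 9.6.** Replace the sentence ruling out imputation with a likelihood-based mixed model using all randomised participants with any available fatigue score (Weeks 0, 8, 10, 14). Add a delta-adjusted or pattern-mixture sensitivity analysis for participants who are alive but lost, over a stated range of shifts that includes 0. Report the Week 10 SD and group difference beside the observed-case values. Report deaths separately and do not impute scores for them. Because a large shift can overstate the SD by as much as informative loss understates it, present the shifts as a range, not as a required planning value.

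2. **Section 9.2.** Name the visit and population for the SD, say that the 10% and 14% figures assume no loss, and restate them for about 37 observed under random loss: about 11% pooled and about 16% per group at 80% confidence.

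3. **Section 10.3.3.** Reword the aim as describing missingness by observed characteristics.

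The cost is a little more analysis and a slightly less favourable stated precision. No new data are needed, since fatigue is already scheduled at all four visits.

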**Specific Aim 2.** A critical element of this proposal is the inclusion of daily (vs. standard recalled) assessments of fatigue, depressive symptoms and proposed mediators, during two 2-week periods in the study (initial: 0-2 weeks, later: 8-10 weeks). Summaries of the proportion and frequency of missing daily assessments will inform the feasibility of collecting this type of data. Graphical displays of these daily reports will prove invaluable for informing both the patterns of the respective symptoms and mechanisms in and of themselves, and also for informing the optimal representation of the patterns in analyses with the recalled measures. Depending on missing data, study group differences in daily (or mean 2-day) values will be evaluated using mixed-effects generalized linear modeling. Findings and effect sizes garnered from these analyses will be compared to those resulting from recalled measures. Informed by the graphical displays, several summary indices of each of the two daily assessment periods (peak value, mean, coefficient of variation) will be generated for use in multi-method, multi-trait analyses of similarities and differences in the patterns of associations among the daily and recalled measures. This analysis will further inform which measures (and/or which summary indices) appear to be the best and most sensitive indices to use in future studies.

**Specific Aim 3:** Open-ended and interview data will be coded by the Qualitative Research Core led by [name] (Collaborator). [name] will consult with the Core to develop a coding system and also code 10% of the responses to assess reliability. Coded responses will be interpreted with a thematic analysis. The number of participants interviewed (20-40) will be decided by when thematic saturation is reached. Qualitative information gained will enrich quantitative results and inform the protocol of a larger trial.

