## 2. BACKGROUND AND RATIONALE

### 2.1 Background on Condition, Disease, or Other Primary Study Focus

**Burden of fatigue and depressive symptoms in gastrointestinal cancers is high.** Gastrointestinal (GI) cancers are among the most prevalent cancers for both men and women, and the number of GI survivors continues to increase. Fatigue, “a subjective state of overwhelming and sustained exhaustion and decreased capacity for physical and mental work that is not relieved by rest,” is reported by a majority (>50%) of patients with GI cancers, co-occurs with other common symptoms such as depression (>30% in patients receiving chemotherapy), and is associated with a decline in post-treatment quality of life. There is overlap in some methods for assessing fatigue and depressive symptoms; however, these symptoms remain moderately correlated even when commonalities are removed. There is also considerable evidence showing that fatigue and depression are distinctly associated with other variables such as quality of life. Further, although chemotherapy is efficacious for increasing survival, it leads to increases in fatigue and depressive symptoms such that symptoms peak approximately 3-5 days following treatment and then improve, however fatigue and depressive symptoms do not return to pretreatment levels in a substantial subset of patients (20-80%). Fatigue and depressive symptoms experienced during treatment are associated with subsequent symptoms. Thus, it is important to address elevations of fatigue and commonly co-occurring depressive symptoms during chemotherapy to improve quality of life in patients with GI cancers.

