## 6.2 Description of Evaluations

Recalled assessments will be collected at four time points (baseline, mid-intervention, post-intervention, 4-week follow-up; Appendix F: Chart Review Form and Questionnaires) and a semi-structured interview conducted after completion of all assessments (either in person or by telephone; Appendix G: Semi-Structured Interview Guide). To minimize burden, all assessments via recalled questionnaires and interviews will be scheduled to coincide with the patients' appointment for chemotherapy.

Therefore, sequencing of each patient's assessments will be based on the timing of the respective patient's first completed chemotherapy visit. The standard chemotherapy timing is every two weeks. The randomized study condition will commence with the second chemotherapy visit. Given that there may be slight personal modifications to the standard schedule, we have proposed a design that will attempt to control for the possible effect of chemotherapy schedule on outcomes. If a chemotherapy visit is rescheduled for within two weeks of the standard schedule, the intervention will occur at that next visit (and all following assessments will then follow the subsequent standard chemotherapy schedule). If the rescheduled chemotherapy visit is more than two weeks later, the in-person study intervention session for that participant will not occur, the assessments will be mailed to the participant for completion, and this will be documented as an aspect of treatment fidelity.

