#### **Baseline Assessments**

For participants who have successfully been screened for eligibility and are enrolled into the study, baseline assessments will be performed.

**Demographics.** Age, race/ethnicity, marital status, education level, ability to pay for the basics, alcohol/substance use and malnutrition status will be self-reported at baseline.

**Clinical Data.** Cancer type, chemotherapy regimen, stage of disease, recurrence status, receipt of other treatments, days since surgery, height, and weight will be abstracted from medical charts at baseline.

**Questionnaire:** Fatigue, Depressive Symptoms, Psychological Stress, Regulation of Psychological Stress, Circadian disruption, and Outcome Expectancies

**Daily Survey (weeks 0-2)** will assess baseline Fatigue and Depressive Symptoms (daily), Psychological Stress (daily), Regulation of Psychological Stress (daily), bedtimes and rising times

**Actigraphy (weeks 0-2)** will assess baseline circadian disruption (daily)

**Blood draws (Inflammation).** Inflammatory cytokines will be assessed at Week 2 prior to starting the intervention.

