### **Randomization**

Randomization will occur the same day that screening is confirmed and will precede intervention initiation by approximately 2 weeks (corresponding with the timing between chemotherapy treatments 1 and 2).

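### Aim 2 sets daily against recalled effect sizes, but the two methods cover different days of the chemotherapy cycle; a matched seven-day fatigue comparison should be added

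*Combined protocol and SAP*

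**What the plan says.** Section 9.6, Specific Aim 2, fits mixed models to arm differences in the daily values and then states: "Findings and effect sizes garnered from these analyses will be compared to those resulting from recalled measures". Separately, it forms the peak, the mean and the coefficient of variation over each whole two-week diary period for a multi-method analysis of associations. The stated use is to inform which measures and indices look most sensitive for later studies.

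The calendar is set elsewhere:

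- Section 6.2: "sequencing of each patient's assessments will be based on the timing of the respective patient's first completed chemotherapy visit", and "The randomized study condition will commence with the second chemotherapy visit". The usual interval between visits is two weeks.
- Section 6.2.2, Randomization: randomization "will precede intervention initiation by approximately 2 weeks (corresponding with the timing between chemotherapy treatments 1 and 2".
- Section 6.2: "all assessments via recalled questionnaires and interviews will be scheduled to coincide with the patients" (the sentence goes on to name the chemotherapy appointment).
- Section 9.5.1: the primary fatigue form has 7 items and looks back seven days.
- Section 6.2.2, Baseline Assessments: the weeks 0-2 survey "will assess baseline Fatigue and Depressive Symptoms (daily), Psychological Stress (daily"; for blood, "Inflammatory cytokines will be assessed at Week 2 prior to starting the intervention".
- Section 2.1: chemotherapy raises fatigue and depressive symptoms, "such that symptoms peak approximately 3-5 days following treatment and then improve".

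Neither the schedule in Section 6.1 nor the constructs table in Section 9.5.2 shows a recalled questionnaire at Week 2. Nothing in Section 9.6 matches the diary days to the recall period or warns that timing and method differ together.

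**The concern.** A comparison of two measurement methods is easiest to interpret when both observe the same days. Here the recalled form is given at the next infusion visit, so it looks back on the late part of a cycle, or at Week 0 on the time before treatment. The diary runs through whole cycles from the infusion onward. Day coverage and reporting method therefore change together.

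What is at stake is the advice carried into the larger trial. If daily fatigue shows the larger arm effect, one explanation is that reporting each day is more sensitive. Another is that the diary included days 3-5 and the recall did not. The second explanation leaves open that a recall form timed to the peak would do as well. The planned comparison cannot tell these apart.

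A smaller version of the problem touches the exploratory mediator work under Aim 1. Cytokine change runs from Week 2 to Week 10, wholly on chemotherapy. Recalled fatigue change from Week 0 to Week 10 also takes in the start of chemotherapy.

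**Working it through.** The plan gives no figure on this point to reproduce. The precision statement for the SD in Section 9.2 has no bearing on it.

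**Step 1: calendar.** Day 0 is the first infusion (Section 6.2: calendar tied to the first visit, study condition starting at the second; Section 6.2.2: Weeks 0 to 2 match the gap between treatments 1 and 2). Cycles last 14 days, so Week 8 is day 56 and Week 10 is day 70. The diaries cover days 0-13 and 56-69. Each recall covers the 7 days before its visit.

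| Recall | Days covered | Position in cycle | Days shared with diary | Peak days (3-5) included |
|---|---|---|---|---|
| Week 0 | -7 to -1 | before first infusion | 0 of 14 (weeks 0-2) | 0 |
| Week 8 | 49 to 55 | days 7-13 | 0 of 14 (weeks 8-10) | 0 |
| Week 10 | 63 to 69 | days 7-13 | 7 of 14 (weeks 8-10) | 0 |

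Each diary period includes all 3 peak days. If the Week 10 recall counts the visit day itself (days 64-70), 6 days are shared instead of 7.

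**Step 2: what timing alone can do to the arm effect.** Assume one instrument for both methods, a recall score that behaves like the average of its seven days, and a true arm effect of 1 unit on certain cycle days and 0 on the others. Let k be the number of effect days in the whole cycle and m the number falling on days 7-13. The daily-mean effect is k/14 and the recall effect is m/7.

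| Effect present on days | Daily mean, k/14 | Recall, m/7 | Recall ÷ daily mean |
|---|---|---|---|
| 3-5 | 3/14 = 0.214 | 0/7 = 0 | 0% |
| 0-6 | 7/14 = 0.50 | 0/7 = 0 | 0% |
| 3-9 | 7/14 = 0.50 | 3/7 = 0.43 | 86% |
| 0-13 | 14/14 = 1 | 7/7 = 1 | 100% |

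In the first row the effect on a single peak day is 1, against 0 in the recall. The shapes are assumptions; the documents give none for the yoga effect.

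**Step 3: baselines.** With baseline adjustment, the residual SD is proportional to √(1 - r²), where r is the baseline-to-outcome correlation. The standardized daily effect relative to recall then changes by √[(1 - r_recall²)/(1 - r_daily²)]. The documents give no correlations. Assuming 0.3-0.5 for the pre-chemotherapy recall baseline and 0.5-0.7 for the on-chemotherapy daily baseline:

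- r_recall = 0.5, r_daily = 0.5: √(0.75/0.75) = 1.00
- r_recall = 0.3, r_daily = 0.7: √(0.91/0.51) = 1.34

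So the baseline mismatch could favor the diary by a factor of 1.00 to 1.34 without any advantage in reporting method.

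**Step 4: after matching.** Limiting the second diary to its last 7 days (63-69) gives 7 of 7 days shared with the Week 10 recall. In every row of Step 2 the restricted daily mean then equals m/7, the recall effect. No restriction can align the baselines, because they share 0 days.

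**The case against.** The strongest reply is that the timing difference is largely the point. Section 2.2 argues that a weekly recall is likely to miss fatigue at its worst and that daily assessment improves on this; Section 9.2 expects daily measures to be more sensitive for the same reason. On that view Aim 2 compares two practical strategies, a diary through the cycle or a form at the clinic visit, and a diary that wins by covering the peak has done its job. This stands, and the full-window comparison should stay. But Section 2.2 also credits daily reporting with less recall bias, and the planned comparison cannot show which of the two advantages produced a gain.

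Several stronger readings are tempting and are not supported:

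- *The arm comparisons are biased.* They are not: the schedule is the same in both arms. Suppose starting chemotherapy raised fatigue by a stable 4 points (assumed; half the 8-point SD in Section 9.2) in both arms. Recalled change would be +4 and daily change 0 within patients, but between arms the shift is 4 - 4 = 0 under recall and 0 - 0 = 0 under the diary.
- *A difference between methods must appear.* With an effect constant over the cycle, and the baseline question set aside, Step 2 gives 1 against 1.
- *The trial will choose its future measure on this result.* Section 9.6 speaks only of informing that choice, for a secondary aim of a 44-patient pilot. It also lets the graphs guide how the daily patterns are represented, so matched days are not excluded; they are simply not specified.
- *All mediator analyses are misaligned.* Recalled stress, stress regulation and circadian measures share Weeks 0, 8, 10 and 14 with recalled fatigue. Only the cytokines differ, and the path analysis is exploratory and conditional.

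**Conclusion.** The point holds as a limit on interpretation. The baseline windows share 0 days. The post-intervention windows share about 7 of 14, with none of the 3 peak days in the recall. If the intervention effect varies over the cycle, a larger daily effect could reflect the days sampled; under the assumed shapes, recall ranges from 0% to 100% of the daily-mean effect from timing alone. The primary analysis is unaffected.

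This rests on 14-day cycles and on the Week 0 form being completed before the first infusion. The latter is inferred from Sections 6.2 and 6.2.2 and not stated outright; if the form were completed on infusion day, a seven-day recall would still be almost wholly pre-infusion. Rescheduled visits or mailed forms would shift individual windows. The point is confined to fatigue, because the protocol text gives a seven-day recall for that measure only.

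**What to change.** In Section 9.6, Specific Aim 2:

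1. Pre-specify a matched-window comparison for fatigue. Set the standardized between-arm effect on the mean of the daily fatigue items, over the seven days before the Week 10 questionnaire, against the standardized between-arm effect on the Week 10 recalled score. Define the seven days from the actual completion date, state how many diary days must be present, and report the post-intervention contrast without baseline adjustment so that it does not depend on the mismatched baselines.
2. Keep the full-window peak, mean and variability, labeled as a comparison of overall assessment strategies.
3. State that the baselines cannot be aligned and that the item sets also differ: 3 daily items, chosen for sensitivity to day-to-day change (Section 9.5.2), against 7 recalled items. The matched comparison removes the timing difference only.
4. For the exploratory associations with cytokines, report change in daily fatigue (weeks 0-2 to 8-10) alongside recalled change. Each diary period ends near a blood draw (Weeks 2 and 10), so this is already aligned.

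These changes cost analysis wording and a few extra estimates; all the data are already in the plan. A recalled form at Week 2 would give a shared on-treatment baseline, at 7 more items for fatigue (17 with the 10-item depression form). It is optional: the current version is dated July 2019, one site is closed to recruitment, and the form would help only participants not yet past that visit.
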